**LY3375880**

Study I9N-MC-FCAB (NCT03334396) is a Phase 2, multicenter, randomized, double-blind, placebo-controlled, parallel-group, outpatient, 60-week study designed to evaluate the efficacy and safety of LY3375880 50-mg, 150-mg, 300-mg, and 600-mg in adult patients with moderate to severe atopic dermatitis.

Eli Lilly and Company  
Indianapolis, Indiana USA 46285  
Protocol I9N-MC-FCAB(b)  
Phase 2

Statistical Analysis Plan electronically signed and approved by Lilly on date provided below.

## **2. Revision History**

Statistical Analysis Plan (SAP) Version 1 is based on Protocol I9N-MC-FCAB(b) and was approved prior to the first production transfer for the internal assessment committee.

### 3. Study Objectives

#### 3.1. Primary Objective

The primary objective of this study is to test the hypothesis that LY3375880 is superior to placebo in the treatment of patients with moderate to severe atopic dermatitis (AD), as assessed by the proportion of patients achieving the validated Investigator's Global Assessment for AD (vIGA-AD, referred to throughout the SAP as IGA) of 0 or 1 with a  $\geq 2$ -point improvement from baseline at Week 16.

#### 3.2. Secondary Objectives

The secondary objectives of the study are the following:

| Objectives   | Endpoints  |
|--|--|
| To compare the efficacy of LY3375880 to placebo as measured by improvement in signs and symptoms at Week 16 in the treatment of subjects with moderate- to- severe AD. | 

Proportion of subjects achieving at Week 16:

EASI-50

EASI-75

EASI-90

SCORAD-75

SCORAD-90

IGA of 0

Mean change from baseline to Week 16 in:

EASI score

SCORAD

Proportion of subjects achieving IGA of 0 or 1 at Week 52

 |
| To characterize the pharmacokinetics of LY3375880 in subjects with moderate-to-severe atopic dermatitisAD  | 

Plasma pharmacokinetic data

  |

### 3.3. Exploratory Objectives

The exploratory objectives of this study are the following:

| Objectives/Endpoints  |
|---|
| 

• To evaluate signs and symptoms, health outcome measures, and QoL measures (total scores, item scores, and derivations) at each time point collected.

• To explore relationships between LY3375880 exposure and study endpoints.

• To characterize post-induction loss of response and maintenance of response.

• To evaluate PD effects of LY3375880 in skin biopsies and peripheral blood.

 |

## 4. Study Design

### 4.1. Summary of Study Design

Study I9N-MC-FCAB(b) (FCAB) is a Phase 2, multicenter, randomized, double-blind, placebo-controlled, parallel-group, outpatient study evaluating the efficacy and safety of LY3375880 subcutaneous (SC) 600 mg every 4 weeks (Q4W), 150 mg Q4W, and 50 mg Q4W as compared to placebo Q4W in adult subjects with moderate-to-severe AD. In addition, LY3375880 300mg Q4W will be evaluated during the maintenance period. The study duration will be up to 65 weeks over 4 study periods:

[figure not shown]
- Period 1: Screening Period lasting from 8 to 35 days prior to Week 0 (baseline, Visit 2).
- Period 2: Induction Period, lasting from Week 0 (baseline, Visit 2) through Week 16 (Visit 8), inclusive.
  - An internal assessment committee will conduct an unblinded interim analysis of efficacy safety data when approximately 40%-60% of patients complete Week 16 (Visit 8). This interim analysis will be conducted for internal decision making to trigger planning activities for future studies associated with LY3375880.
- Period 3: Maintenance Period, lasting from Week 20 (Visit 9) through Week 52 (Visit 17), inclusive. At Week 20, the following will occur:
  - Responders (defined as having achieved a 50% reduction in the Eczema Area and Severity Index score [EASI-50] response, regardless of whether rescue therapy has been initiated) will undergo the following re-randomizations:
    - Subjects on any dose of LY3375880 will be re-randomized at a 2:1 ratio to either maintain their current regimen or to receive placebo until loss of response (not achieving a 25% reduction in the EASI score [EASI-25] at a scheduled visit), at which point they will restart their induction period regimen.
    - Subjects on placebo will continue receiving placebo until loss of response, at which point they will receive LY3375880 300 mg Q4W.
  - Nonresponders will undergo the following re-randomizations/reassignments:
    - Subjects on 50 mg Q4W will be reassigned to 150 mg Q4W
    - Subjects on 150 mg Q4W will be reassigned to 600 mg Q4W
    - Subjects on 600 mg Q4W will remain on their current regimen
    - Subjects on placebo will receive LY3375880 300 mg Q4W.
  - Subjects with persistent disease activity defined as not achieving EASI-25 for 3 consecutive maintenance period visits, or 8 maintenance period weeks (whichever is longer) not already on 600 mg Q4W will be reassigned to 600 mg Q4W for the remainder of the study.
- Period 4: Post-Treatment Follow-Up Period, spanning approximately 8 weeks from Week 52 (Visit 17) to Week 60 (Visit 801).

Approximately 200 subjects will be randomized 1:1:1:1 at Week 0 to 1 of 4 treatment groups: placebo SC (Q4W), LY3375880 SC 600 mg (Q4W), LY3375880 150 mg (Q4W), or LY3375880

50 mg (Q4W). The study duration will be up to 65 weeks (Screening Period: Up to 5 weeks; Induction Period: 16 weeks; Maintenance Period: 36 weeks; Follow-up Period: 8 weeks).

Subjects will be stratified at randomization according to disease severity (IGA [3 versus 4]) and geographic region (Japan versus Rest of World).

Figure FCAB.4.1 illustrates the study design. The blinding procedure is described in the Protocol.

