IL-19, TARC, Periostin		X		X	X	X		X		X		X		X		X	X	
Flow cytometry sample		X			X			X									X	

Abbreviations: AD = atopic dermatitis; BP = blood pressure; C-SSRS = Columbia-Suicide Severity Rating Scale (11 categories of suicidal ideation/suicidal behavior); DLQI = Dermatology Life Quality Index; DNA = deoxyribonucleic acid; EASI = Eczema Area and Severity Index; ECG = electrocardiogram; EDTA = ethylenediaminetetraacetic acid; ePRO = electronic subject-reported outcomes (device); ET = early termination; FSH = follicle-stimulating hormone; HBcAb = hepatitis B core antibody; HBsAb = hepatitis B surface antibody; HBsAg = hepatitis B surface antigen; HBV = hepatitis B virus; HCV = hepatitis C virus; HIV = human immunodeficiency virus; IGA = Investigator's Global Assessment; IgE = immunoglobulin E; IL = interleukin; IP = investigational product; IWRS = interactive web-response system; NRS = Numeric Rating Scale; PK = pharmacokinetic; POEM = Patient-Oriented Eczema Measure; PPD = purified protein derivative; RNA = ribonucleic acid; SC = subcutaneous; SCORAD = SCORing AD; TARC = thymus and activation-regulated chemokine; TB = tuberculosis.

- a The symptom-directed physical examination may be conducted at the investigator's discretion any time a subject presents with physical complaints.
- b Subjects will be re-randomized/reassigned at Week 16 as described in Section 5.
- c Will be collected as electronic Clinical Outcome Assessment (eCOA) data.
- d The following measures (POEM and DLQI) should be completed by the subject prior to any clinical assessments being performed on days when study visits occur.
- e Will be collected daily via an electronic subject diary.
- f The Self-Harm Follow-up Form is only required if triggered by the Self-Harm Supplement Form.
- g A posterior–anterior and lateral chest x-ray will be performed at screening unless one has been performed within the past 90 days, the x-ray and reports are available, and a repeat chest x-ray is not clinically indicated per investigator judgment.

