5.1. Overall Design

Study I9N-MC-FCAB (FCAB) is a Phase 2, multicenter, randomized, double-blind, placebo-controlled, parallel-group, outpatient study evaluating the efficacy and safety of LY3375880 SC 600 mg Q4W, 150 mg Q4W, and 50 mg Q4W as compared to placebo Q4W in adult subjects with moderate-to-severe AD. In addition, LY3375880 300mg Q4W will be evaluated in the maintenance period as described below.

The study duration will be up to 65 weeks over 4 study periods:

- Period 1: Screening Period lasting from 8 to 35 days prior to Week 0 (baseline, Visit 2).
- Period 2: Induction Period, lasting from Week 0 (baseline, Visit 2) through Week 16 (Visit 8).
- Period 3: Maintenance Period, lasting from Week 16 (Visit 8) through Week 52 (Visit 17, inclusive). At Week 16, the following will occur:
 - Responders (defined as having achieved a 50% reduction in the Eczema Area and Severity Index score [EASI-50] response, regardless of whether rescue therapy has been initiated) will undergo the following re-randomizations:
 - Subjects on any dose of LY3375880 will be re-randomized at a 2:1 ratio to either maintain their current regimen or to receive placebo until loss of response (not achieving a 25% reduction in the EASI score [EASI-25] at a scheduled visit), at which point they will restart their induction period regimen.
 - Subjects on placebo will continue receiving placebo until loss of response, at which point they will be reassigned to receive LY3375880 at 300 Q4W.
 - Nonresponders will undergo the following reassessments:
 - Subjects on 50 mg Q4W will be reassigned to 150 mg Q4W.
 - Subjects on 150 mg Q4W will be reassigned to 300 mg Q4W.
 - Subjects on 600 mg Q4W will remain on their current regimen.
 - Subjects on placebo will be reassigned to receive 300 mg Q4W.
 - Subjects with persistent disease activity, defined as not achieving EASI-25 for 3 consecutive scheduled maintenance period visits, not already on 600 mg Q4W will be reassigned to 600 mg Q4W for the remainder of the study.
- Period 4: Post-Treatment Follow-Up Period, spanning approximately 8 weeks from Week 52 (after Visit 17) to Week 60 (Visit 801).

Rescue therapy is permitted starting at Week 8 for subjects who do not achieve an EASI-25 response. Refer to Section [7.7.3](#) for details.

Treatment Arms and Duration:

[figure not shown]

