### **5.2.1. Analysis Populations**

**Enrolled population:** The enrolled population is defined as all participants who sign informed consent.

**Intent-to-treat (ITT) population:** The ITT population analysis set is defined as all randomized patients, even if the patient does not take the assigned treatment, does not receive the correct treatment, or otherwise does not follow the protocol.

**Per-Protocol (PPS) population:** The PPS populations is defined as all randomized patients who do not commit an Important Protocol Deviation (IPD) that could potentially compromise efficacy results.

**Safety population:** The safety population is defined as all randomized patients who receive at least 1 dose of their assigned double-blind study treatment..

**Maintenance Period Population:** All ITT patients who received at least one dose of study treatment and have entered the maintenance period at Week 16 (Visit 8).

Unless otherwise specified, the efficacy and health outcome analyses will be conducted on the ITT population (Gillings and Koch 1991), which seeks to preserve the benefits of randomization and avoid the issue of selection bias. Patients will be analyzed according to the treatment to which they were randomized.

Safety analyses will be done on the safety population. Patients will be analyzed according to the dosing regimen to which they were assigned. Analyses of the safety endpoints, many of which are incidence based, will include all patients in the safety population, unless specifically stated otherwise.

In the rare situation where a patient is Lost to Follow-up at the first postbaseline visit, but some safety data exists (eg, unscheduled laboratory assessments) after first dose of study drug, a listing of the data or a patient profile will be provided.

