### **5.2.2.2. Maintenance Period Considerations**

The baseline value for the safety analyses will be the last available value before the intial dose in the Maintenance period (expected at Week 16, Visit 8). Other definitions of baseline value, such as the last measurement on or prior to reassignment to active treatment, may be used to conduct additional supporting analyses.

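### SAP 4.1 disagrees with Protocol 5.1 on the 150-mg nonresponder regimen and the maintenance start, and the SAP's as-randomised rule cannot form the 300-mg group listed for Week 52

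*SAP*

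**What the plan says.** SAP section 2 names Protocol I9N-MC-FCAB(b) as its basis, and the protocol supplied is amendment (b). The differences below are therefore between current texts.

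- **Regimen for 150-mg nonresponders.** SAP 4.1: "Subjects on 150 mg Q4W will be reassigned to 600 mg Q4W". Protocol 5.1: "Subjects on 150 mg Q4W will be reassigned to 300 mg Q4W". The rules for nonresponders on 50 mg, 600 mg and placebo agree.
- **Start of maintenance.** SAP 4.1: "Period 3: Maintenance Period, lasting from Week 20 (Visit 9) through Week 52 (Visit 17), inclusive. At Week 20, the following will occur". Protocol 5.1: "Period 3: Maintenance Period, lasting from Week 16 (Visit 8) through Week 52 (Visit 17, inclusive). At Week 16, the following will occur". Footnote b of the protocol's Schedule of Activities: "Subjects will be re-randomized/reassigned at Week 16 as described in Section 5".
- **Timing elsewhere in the SAP.** Section 4.1 itself gives "Induction Period: 16 weeks; Maintenance Period: 36 weeks; Follow-up Period: 8 weeks". The Maintenance Period Population in SAP 5.2.1 consists of patients who "have entered the maintenance period at Week 16 (Visit 8". SAP 5.2.2.2 takes the safety baseline before the initial dose "in the Maintenance period (expected at Week 16, Visit 8". SAP 5.9 measures maintenance compliance from Week 16 to Week 52.
- **Week 52 groups.** SAP Table FCAB.5.2 has a secondary row in the Maintenance population that compares 600, 300, 150 and 50 mg with placebo at Week 52.
- **Grouping rules.** SAP 5.2.1 analyses efficacy by randomised treatment and safety by assigned regimen. SAP 5.13 analyses safety by the product randomised at Week 0.
- **Status of the analysis.** Protocol 10.2.1.2 calls maintenance analyses exploratory and descriptive. Protocol 10.2.3.2 nevertheless lists IGA 0 or 1 at Week 52 under the logistic model.

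**The concern.** In its visible text, SAP 4.1 is the only part of the SAP that sets out the reassignment rules (its design figure is not reproduced). A programmer who builds maintenance groups from it would get a different scheme from the protocol's for one of the four arms, and a start date four weeks later than the rest of the SAP uses.

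The second problem would remain after those two corrections. The Week 52 row needs a 300-mg group, and no stated rule produces one. The SAP also does not say where to count patients withdrawn to placebo, retreated after loss of response, or escalated to 600 mg. The same gap affects maintenance compliance (SAP 5.9) and exposure (SAP 5.13.1), both summarised by treatment group. Protocol 10.2.8 plans the primary database lock once induction is complete, so a label left undefined could be chosen after Week 16 results are known.

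**Working it through.** **1. Maintenance length.** Inputs from both documents: screening up to 5 weeks, induction 16, maintenance 36, follow-up 8, total up to 65.

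- Stated total: 5 + 16 + 36 + 8 = 65. This reproduces.
- Start at Week 16: 52 − 16 = 36 weeks, equal to the stated length.
- Start at Week 20: 52 − 20 = 32 weeks, and 5 + 16 + 32 + 8 = 61. Because SAP 4.1 ends induction at Week 16, Weeks 16 to 20 then belong to no period.

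**2. Can the as-randomised rule give a 300-mg group?**

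- Week 0 randomisation offers placebo, 50, 150 or 600 mg.
- Re-randomisation of active-arm responders offers the current regimen or placebo.
- 300 mg is reached only by reassignment: placebo nonresponders and placebo patients who lose response under both texts, plus 150-mg nonresponders under Protocol 5.1.

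Nobody is randomised to 300 mg at either stage, so the rule gives a group of size 0 under either text.

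**3. Patients whose class at maintenance entry depends on the text followed.** The documents give 50 per arm but no EASI-50 rates, so the rates are assumptions. With no dropout and EASI-50 rate r at 150 mg, the number is 50 × (1 − r):

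- r = 30%: 50 × 0.70 = 35
- r = 50%: 50 × 0.50 = 25
- r = 70%: 50 × 0.30 = 15

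To show the effect on group size, assume the same r in all active arms and a placebo rate rp. The expected 300-mg group at entry is 50 × (1 − rp) under SAP 4.1, and 50 × (1 − rp) + 50 × (1 − r) under Protocol 5.1.

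| r | rp | 300 mg, SAP 4.1 | 300 mg, Protocol 5.1 | Difference |
|---|---|---|---|---|
| 30% | 15% | 42.5 | 77.5 | 35 |
| 50% | 25% | 37.5 | 62.5 | 25 |
| 70% | 40% | 30 | 45 | 15 |

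Under SAP 4.1 the same 35, 25 or 15 patients sit in the 600-mg group instead. These are upper limits: dropout lowers them, and by regimen held at Week 52 the difference can only shrink, because both texts move persistent disease to 600 mg.

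**4. Who is compared with whom.** At entry, under either text, everyone on 300 mg is an EASI-50 nonresponder. Everyone on placebo is an EASI-50 responder, either a placebo responder or an active-arm responder withdrawn to placebo. A 300-mg versus placebo contrast by entry regimen therefore compares patients selected on opposite outcomes.

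**5. Power.** Enumerating the two-sided Fisher's exact test at 36% versus 8% with 50 per arm gives 91.4%, consistent with the stated minimum of 90%. It concerns Week 16 and is not touched by this point.

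**The case against.** **Dosing does not follow the SAP.** SAP 4.2 has the IWRS assign product, and Protocol 7.2.1 has dose times recorded. This stands. A reader might infer that patients were given or labelled with the wrong dose; the documents do not support that, because a conflict in a design summary does not show how the IWRS was configured. But IWRS records cannot say which of several assignments defines the analysis group.

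**Maintenance is exploratory and descriptive.** Protocol 10.2.1.2 says so, and it limits the stakes. Yet Protocol 10.2.3.2 and SAP Table FCAB.5.2 treat Week 52 as a secondary analysis, the former under the logistic model, and a descriptive table by dose still needs defined dose groups.

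**The Week 52 row may depart from the default.** The as-randomised sentence follows a clause allowing exceptions, and the row names its own population and a 300-mg group. That is a fair reading, but no substitute rule appears in the visible text.

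**The persistent-disease trigger also differs.** SAP 4.1 adds an eight-week alternative and drops the restriction to scheduled visits. A reader might count this as a further material conflict. Maintenance visits are four weeks apart, so three consecutive visits nominally span eight weeks; only visit windows or unscheduled visits could separate the wordings. The point does not rest on it.

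**Conclusion.** The two contradictions are plain on the text, and on timing the SAP also contradicts itself. The undefined maintenance label is a separate gap and the more substantive one, because the stated rule cannot produce a group that the SAP's own table lists.

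A reader might infer that the Week 16 primary result is at risk. It is not: that analysis uses the Week 0 arms. Nor is the exposure confined to the Week 52 comparison, since maintenance compliance and exposure are also reported by treatment group and the two safety grouping rules differ.

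The size, at most 35 to 15 of 50 patients classed differently at entry, rests on assumed EASI-50 rates of 30% to 70% at 150 mg and no dropout. It illustrates the scale and is not an estimate from the documents. The change should be made, but it does not threaten the trial's main conclusion.

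**What to change.** 1. Reconcile SAP 4.1 with Protocol 5.1 on the 150-mg nonresponder regimen and the maintenance start, and use one start throughout the SAP. This review takes no position on which regimen or week is right. The trigger wording can be aligned in the same edit.
2. For Week 52 and every other maintenance summary, replace the as-randomised rule with one explicit label, for example the sequence of Week 0 arm and maintenance assignment taken from IWRS assignments. Make the groups in Table FCAB.5.2 match it, and settle the safety grouping between SAP 5.2.1 and 5.13.
3. State that groups formed by response-based reassignment are not randomised comparisons with placebo.
4. Correct the Week 52 row of Table FCAB.5.2, which names IGA of 0, whereas Protocol 10.2.3.2 and SAP 3.2 give IGA 0 or 1. Its method cell appears blank, which may only reflect how the table was extracted.

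The cost is SAP text and programming specification, ideally before Week 52 programming. No new data are needed, and sample size and alpha do not change.

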**Figure FCAB.4.1. Illustration of study design for Clinical Protocol I9N-MC-FCAB.**

Abbreviations: PBO = placebo; QD = once every four weeks; W = week.

## 4.2. Method of Assignment to Treatment

Subjects who meet all criteria for enrollment will be randomized 1:1:1:1 to double-blind treatment at Visit 2. Assignment to treatment groups will be determined by a computer-generated random sequence using an interactive web-response system (IWRS). The IWRS will be used to assign vials containing double-blind IP to each patient. Site personnel will confirm that they have located the correct vials by entering a confirmation number found on the vials into the IWRS. The IWRS will be used to assign IP to each patient. Site personnel will confirm that they have located the correct packages by entering a confirmation number found on packages into the IWRS.

To achieve between-group comparability, the randomization will be stratified by IGA (3 versus 4) and by geographic region (Japan versus Rest of World).

## 5. A Priori Statistical Methods

### 5.1. Determination of Sample Size

Study I9N-MC-FCAB(b) will aim to enroll approximately 200 patients  $\geq 18$  years of age. Assuming 36% and 8% of subjects achieve an IGA score of 0 or 1 (clear or almost clear skin) and  $\geq 2$ -point improvement from baseline at Week 16 for LY3375880 and placebo, respectively, pairwise comparisons to placebo have at least 90% power using a 2-sided Fisher's exact test at the 0.05 significance level, with no adjustment for multiple comparisons.

Sample size and power estimates were obtained from R version 3.4.3.

### 5.2. General Considerations

This plan describes *a priori* statistical analyses for efficacy, health outcomes, and safety that will be performed.

Statistical analysis of this study will be the responsibility of Eli Lilly and Company (Lilly). The statistical analyses will be performed using SAS® Version 9.4 or higher.

Not all displays described in this SAP will necessarily be included in the clinical study report (CSR). Not all displays will necessarily be created as a “static” display. Some may be incorporated into interactive display tools instead of or in addition to a static display. Any display described in this SAP and not included in the CSR would be available upon request.

For continuous measures, summary statistics will include sample size, mean, standard deviation (SD), minimum, median, and maximum. The 1st quartile and 3rd quartile may also be presented. The minimum and maximum will be reported to the same number of decimal places as the raw data recorded in the database. The mean, 1st quartile, median, 3rd quartile, and SD will generally be reported to 1 more decimal place than the raw data recorded in the database. In general, the maximum number of decimal places reported shall be 4 for any summary statistic. For categorical measures, summary statistics will include the sample size, frequency count, and percentage. Percentages will be presented to 1 decimal place unless otherwise stated.

Percentages will not be presented for zero counts. Incidence rates and 95% confidence interval (CI) will be displayed for select safety endpoints.

Statistical tests of treatment effects and CIs will be performed at a 2-sided significance level of 0.05, unless otherwise stated.

All p-values will be rounded up to 3 decimal places. For example, any p-value strictly greater than 0.049 and less than or equal to 0.05 will be displayed as 0.050. This guarantees that on any printed statistical output, the unrounded p-value will always be less than or equal to the displayed p-value. A displayed p-value of 0.001 will always be understood to mean  $\leq 0.001$ . Likewise, any p-value displayed as 1.000 will be understood to mean  $> 0.999$  and  $\leq 1$ .

Data collected at early termination visits will be mapped to the next scheduled visit number for that patient if it falls within the visit window as discussed in Section 5.2.2. For by-visit summaries, only visits in which a measure was scheduled to be collected will be summarized. Any unscheduled visit data will be included at the patient-level listings. However, the data will

still be used in other analyses, including shift analyses for safety analytes, change from baseline to endpoint using modified last observation carried forward (mLOCF) analyses, and other categorical analyses.

